6.1.1 Primary Outcome

6.1.1.1. Original Design Assumptions

Of the 16 VAHCS in VHA region 16 and 21, 10 VAHCS agreed to participate in the study, with an average of 9 to 10 clinics per VAHCS, and an average of at least 1,000 Veterans per clinic. These numbers were based on conservative projections of the number of Veterans at the time of randomization and account for missing vaccination (i.e., misclassification) status for Veterans who may have been vaccinated outside of the VA. We hypothesize that the larger proportion of Veterans will get vaccinated (both first and fully) within 12 months in the VAI arm compared to usual care. Calculations were conducted with PASS 19 (Kaysville, Utah) using sample size for mixed models for two sample proportions with a 3-level hierarchical design assuming an intra-cluster correlation (ICC) of 0.07 for individuals within a clinic and an ICC of 0.02 for clinics within a VAHCS [Elley CR, et al. (2005)]. With a type I error rate of 0.05 (two-sided) we will have at least 90% power to detect between a 9.6% and 14.6% difference in vaccination rates assuming a rate in the usual care group ranging from 5% to 20% and a total sample size of 90,000 to 100,000. **Table 1** shows details of different scenarios.

Table 1: Detectable difference for comparing 2 proportions in a hierarchical model assuming 5 VAHCS per arm with on average 9-10 clinics per VAHCS and on average 1000 individuals per clinic, 90% power, type I error of 5% (two-sided) and level 1 ICC of 0.07 and level 2 ICC of 0.02

Total Sample Size	Clinics VAMC*	Rate in Usual	Detectable
		Care	difference
90,000	9	5%	9.7%
100,000	10	5%	9.6%
90,000	9	10%	12.0%
100,000	10	10%	11.8%
90,000	9	15%	13.5%
100,000	10	15%	13.3%
90,000	9	20%	14.6%
100,000	10	20%	14.4%

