6.1.1.2 Actual Design Parameters

Of the 16 VAHCS in VHA region 16 and 21, 10 VAHCS agreed to participate in the study (5 per arm), with median number of 9 clinics per VAHCS (range: 4 to 12) with total sample size of 338,718 (Usual Care: 190,427; Intervention: 148,291) eligible Veterans at the start of the study at each VAHCS.

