Second, VHA has been developing a health information exchange with state Immunization Information Systems (IIS) in partnership with CDC to query and report Veteran immunization records. This exchange, known as the IZ Gateway, began querying state registries for 9 of the 10 study sites during July and August of 2023. Unfortunately, VHA does not plan to query state registries retrospectively for all Veterans. Instead, VHA will query individual Veterans' records when they receive VA health services. Accordingly, we anticipate differential vaccine ascertainment in which Veterans who receive care from the time the Gateway was activated in their home state until the final data lock for this study will have near-complete vaccine ascertainment; in contrast, Veterans who do not receive care during this period will have less-complete ascertainment. Vaccine records populated through the Gateway can be identified which will help us to evaluate potential biases resulting from the timing of the Gateway rollout. For the main analyses, records populated through the IZ Gateway are being removed from the analytic dataset to avoid differential bias.

Due to limitations of the IZ Gateway and Medicare data, we will utilize one or more of several methods to ascertain the missing vaccination records and its impact on our estimates. These include comparison of our rates to those published by state and federal authorities for our VISNs or comparison of our rates to those reported by national and local VA dashboards. Alternatively, to estimate population levels of underreporting, we may need to utilize survey sampling methodology and probability weighting to randomly survey Veterans with no documentation of COVID vaccination. In sum, primary analyses for Aim 1 will utilize only VA electronic health data to ascertain Veterans' vaccination status. We will also conduct sensitivity analyses that incorporate all available data sources (e.g., electronic health records; Medicare; state-level records; IZ Gateway).

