9.1.4.1 Expanding Analyses to Include Vaccination Records from Medicare/Medicaid and IZ Gateway

We plan to incorporate the vaccination records from Medicare/Medicaid and the IZ gateway and run sensitivity analyses for the primary outcome. These supportive analyses will provide variation in the estimated intervention effect related to incorporating external sources of vaccination records. On account of the IZ Gateway querying state IIS records on a prospective basis, these sensitivity analyses will focus on Veterans who have received care since the IZ Gateway was activated in their home states, which for the study sites happened during July or August of 2023. The specified statistical model is identical to that laid out in Section 9.1.4.

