9.1.5.1 Expanding Analyses to Vaccination Records from Medicare/Medicaid and IZ Gateway

We plan to incorporate the vaccination records from Medicare/Medicaid and the IZ gateway and run sensitivity analyses for the secondary outcome. The motivation and analysis model are identical to that laid out in Section 9.1.4.1. We will include Veteran records provided by these additional data sources who were not reported to have completed or initiated the primary series at randomization.

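### The IZ Gateway sensitivity analysis is written as if all ten sites were connected in July or August 2023, but the SAP says nine were, and no rule covers the tenth

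*SAP*

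**What the plan says.** SAP 9.1.3 explains that the IZ Gateway "began querying state registries for 9 of the 10 study sites during July and August of 2023". A Veteran's registry record is pulled only when that Veteran comes in for VA care, so capture depends on who was seen after activation. For that reason the section adds: "For the main analyses, records populated through the IZ Gateway are being removed from the analytic dataset to avoid differential bias".

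SAP 9.1.4.1 then plans a supportive analysis of the primary outcome that brings in Medicare/Medicaid and Gateway records. On its population it says that "these sensitivity analyses will focus on Veterans who have received care since the IZ Gateway was activated in their home states", and on timing, "which for the study sites happened during July or August of 2023". It makes no exception for any site. On the model: "The specified statistical model is identical to that laid out in Section 9.1.4". SAP 9.1.5.1 carries this to the secondary outcome: "The motivation and analysis model are identical to that laid out in Section 9.1.4.1".

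Protocol 5.9 contains both the nine-of-ten statement and the unqualified one. SAP 6.1.1.2 gives ten randomized health care systems, five per arm. SAP 8.1 sets the database freeze at 10/19/2023.

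**The concern.** The two SAP sections cannot both be right about the tenth site, and the one that defines the analysis is the one that overlooks it. An analyst working from 9.1.4.1 has to improvise, and two readings are available.

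- **Apply the home-state rule literally.** Veterans whose state had no activation cannot qualify, so most or all of the tenth site leaves the analysis.
- **Apply a July–August 2023 date to every site.** The tenth site stays in, without Gateway records, and is compared with sites whose recent attenders have nearly complete records.

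Each site belongs wholly to one arm, so either reading acts on one arm only. The purpose of the analysis is to show how far the estimate moves when outside records are added. If it does move, a reader could not tell better capture from a changed set of clusters or from uneven capture between sites.

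**Working it through.** **1. The passages side by side**

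| Item | SAP 9.1.3 | SAP 9.1.4.1 |
|---|---|---|
| Sites with activation in July–August 2023 | 9 of 10 | the study sites, no exception |
| Rule for the tenth site | none | none |
| Model | Gateway records removed from main analyses | unchanged 9.1.4 model |

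10 − 9 = 1 site: 10% of the clusters and 1 of the 5 in its arm.

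**2. If the tenth site drops out (5 v 4)**

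Take equal cluster weights and a common between-cluster variance. The variance of the arm difference is then proportional to 1/k₁ + 1/k₂.

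- Unstratified: √[(1/5 + 1/4)/(1/5 + 1/5)] = √(0.45/0.40) = 1.061.
- Stratified by VISN: the states in SAP Table 2, with the VISN areas in Protocol 5.2.b, give 4 sites in VISN 16 and 6 in VISN 21. Assume an even split, 2 v 2 and 3 v 3. The stratum information is 1/(1/2 + 1/2) = 1 and 1/(1/3 + 1/3) = 1.5, total 2.5.
  - Lose a VISN 16 site: 1/(1/2 + 1) = 0.667, total 2.167, SE ratio √(2.5/2.167) = 1.074.
  - Lose a VISN 21 site: 1/(1/3 + 1/2) = 1.2, total 2.2, SE ratio √(2.5/2.2) = 1.066.

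So the standard error rises by about 6 to 7%. Before site-level covariates, cluster degrees of freedom go from 10 − 2 = 8 to 9 − 2 = 7.

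**3. The same loss on the scale of the plan's own power table**

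Inputs from SAP 6.1.1.1: M = 1,000 Veterans per clinic, C = 9 or 10 clinics, ICCs 0.07 and 0.02, two-sided 5%, 90% power.

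- Design effect = 1 + (M − 1)(0.07) + M(C − 1)(0.02). For C = 9 this is 1 + 69.93 + 160 = 230.9; for C = 10 it is 250.9.
- Detectable difference d solves d = 1.96·SE₀ + 1.2816·SE₁, with pooled variance in SE₀, unpooled variance in SE₁, and both variances multiplied by the design effect.
- Check at 5% usual care, 9 clinics, 45,000 per arm: SE₀ = 0.0302, SE₁ = 0.0298, so d = 0.0592 + 0.0382 = 0.0974, or 9.7%. All eight rows of SAP Table 1 reproduce to the printed decimal.

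With 45,000 in one arm and 36,000 in the other (9 clinics per site):

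| Usual-care rate | 5 v 5 | 5 v 4 (range over which arm loses the site) |
|---|---|---|
| 5% | 9.7% | 10.4–10.6% |
| 10% | 12.0% | 12.8–12.9% |
| 15% | 13.5% | 14.3–14.4% |
| 20% | 14.6% | about 15.5% |

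The rise is about 0.7 to 1.0 points. Power at the tabulated differences falls from about 90% to 85–88% (unpooled variance). This is only a yardstick: Table 1 was made for the primary analysis, and the sensitivity analysis was not separately powered. The normal quantiles used here do not reflect the lost degree of freedom.

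**4. If the tenth site is kept without Gateway records**

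Let u be the points of recorded uptake that Gateway records add at a connected site. With five equally weighted sites per arm, the arm difference shifts by u/5. The documents give no value for u. As an assumed range, u = 2, 5, 10 and 20 points gives 0.4, 1, 2 and 4 points. The direction depends on the tenth site's arm, which is not stated.

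**5. Room for a different activation date**

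From 1 July 2023 to the 10/19/2023 freeze is 110 days; from 31 August it is 49. A later activation before the freeze is possible, and 9.1.3 does not exclude an earlier one.

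**The case against.** The case for leaving this alone has real substance.

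- **The count is disclosed.** SAP 9.1.3 gives nine of ten just ahead of the analyses that use it, and says Gateway records can be identified so that rollout bias can be examined. Nothing is hidden; the gap is that 9.1.4.1 does not act on the count.
- **The site need not be lost.** A reader might infer that a whole cluster certainly leaves the analysis. The documents do not establish this. The tenth site could have been activated outside July–August 2023, and eligibility runs by home state, so some of its Veterans may live in a connected state.
- **Bias is not the literal reading.** A reader might infer that the analysis will introduce a bias of known size. The home-state rule points to exclusion, so uneven capture arises only if a common date is imposed. Any figure also needs uptake and capture rates that the documents do not give.
- **The site cannot be identified.** If the feed works state by state, SAP Table 2 might suggest a state with a single site (Hawaii, Louisiana or Texas). That is inference only.
- **Only supportive analyses are touched.** Gateway records are out of the main analyses, and the misclassification model in SAP 9.1.4.2 works by clinic without depending on Gateway connection.

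All of this limits the size of the problem. None of it supplies a rule for the tenth site, and whatever that site's status, the sentence in 9.1.4.1 conflicts with 9.1.3.

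**Conclusion.** The point holds as an internal contradiction with a missing rule, confined to the Gateway sensitivity analyses of the primary and secondary outcomes. On the literal reading, and if the tenth site's state was not activated before the freeze, the comparison becomes about 5 v 4. That widens the standard error by 6 to 7%, assuming equal cluster weights and, for the stratified figures, an even split within VISN. On the common-date reading, one site in one arm is recorded less completely than the others, by an amount the documents do not allow anyone to fix. A reader should not infer that the primary result is threatened. It is worth correcting because, as written, a shift between the main and Gateway estimates could not be attributed to better capture.

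**What to change.** 1. In SAP 9.1.4.1 and the matching paragraph of Protocol 5.9, change the activation statement to nine sites. Name the tenth site and give its arm and its activation date or status.
2. State the rule. If the tenth site was not activated before the 10/19/2023 freeze, exclude it explicitly from the Gateway analysis and report clusters per arm (5 v 4). If it was activated on another date before the freeze, give that date and let its Veterans enter under the same home-state rule.
3. Beside the Gateway result, report the 9.1.4 model with VA-only records on exactly the same Veterans: same connected sites, same care-since-activation restriction. The contrast between the two then reflects the data source alone, while the contrast between this VA-only run and the main analysis shows the effect of the narrower population.
4. Do the same for SAP 9.1.5.1.

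The cost is wording, one extra model run per outcome, and a slightly wider interval in the sensitivity analysis if the site is excluded. SAP section 9 allows changes up to final data lock and before unblinding. If that point has passed, make the same clarification in the report and label it post hoc.

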9.1.4.2 Missing Outcomes/Misclassification of Vaccination Status

We will conduct sensitivity analyses with a Bayesian form of multi-level logistic regression that uses the same core hierarchical model in Section 9.1.4 [Polson et al. (2013)]. Bayesian methods estimate parameter values (e.g., odds ratio of vaccine uptake between intervention arms) by summarizing sequentially drawn values from probability distributions with parameters updated jointly by the observed data (vaccination counts, clinic, and VAMC characteristics, etc.) and updated values of other model parameters. For our needs, the Bayesian logistic regression will incorporate a *multiple imputation* step that corrects the observed vaccination rates in two different ways. We can correct the total number of eligible Veterans, i.e., the denominator at each facility due to misclassifying them as unvaccinated prior to study start. Second, we can correct the count of observed vaccinations over the course of the study at each study site, i.e., the numerator, due to imperfect vaccination records ascertainment.

For the primary aim, we assume no uncertainty in Veteran eligibility since we will be using all Veterans with at least one primary care visit. This entails not subtracting a modeled probabilistic number of Veterans from the denominator of the rate of vaccination per facility, whereas the multiple imputation adds a *random quantity* to the count of instances of any vaccine dose (i.e., the numerator) to represent the unknown vaccinations over the course of the study that, if ignored, would be labeled as unvaccinated in the eligible sample.

Each clinic's corrected quantity will be equal to a probabilistically modeled rate of misclassified vaccinations multiplied by the count of those Veterans labeled as unvaccinated according to the available data. The distribution for each timepoint's rate of misclassified vaccinations will be assumed to follow a truncated Beta distribution with a lower bound estimated from available Medicare data from 2021-2022, upper bound, mode (most likely value), lower and upper percentile values determined by investigators. The Bayesian framework then updates the model's parameters with these corrected vaccination counts instead of the observed vaccination counts. We will assess changes in the parameter estimates across a range of assumptions for the two misclassification rates and summarize the results with posterior probabilities of a non-null intervention effect, 95% credible intervals, and posterior means and medians.

9.1.5 Analysis of Secondary Outcome

We will use the same hierarchical, multi-level method for binary outcomes to analyze the secondary outcome of primary series completion in Veterans reported to not have initiated or completed the COVID-19 primary series at randomization. The model structure and adjustments are identical to that

for the primary outcome in Section 9.1.4. No multiple testing will be considered since there is only one secondary outcome. We will report the difference in rates between the VAI and usual care arms and the 95% confidence interval.

Sensitivity Analyses

9.1.5.1 Expanding Analyses to Vaccination Records from Medicare/Medicaid and IZ Gateway

We plan to incorporate the vaccination records from Medicare/Medicaid and the IZ gateway and run sensitivity analyses for the secondary outcome. The motivation and analysis model are identical to that laid out in Section 9.1.4.1. We will include Veteran records provided by these additional data sources who were not reported to have completed or initiated the primary series at randomization.

9.1.5.2 Missing Outcomes/Misclassification of Vaccination Status

We will use the Bayesian multiple imputation model described in Section 9.1.4.3 for the secondary outcome for the same motivations described therein. Due to the uncertainty in the definition of the eligibility, that is, knowing with 100% certainty that a Veteran did not complete the vaccine primary series prior to study start, the total count of eligible Veterans at each clinic (i.e., the denominator) will be reduced by a *random* quantity to represent the count of Veterans who were misclassified as having not completed the primary series at or before baseline. Thereafter, we will correct the count of observed primary series completions by adding a *random* value to represent the unknown primary series completions over the course of the study that, if ignored, would be labeled as incomplete primary series in the eligible sample. Analytical summaries will be identical to those laid out in Section 9.1.4.2.

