- H1b: A greater incidence of previously unvaccinated Veterans that completes COVID-19 primary vaccination (2 doses of mRNA vaccine or 1 dose of Janssen (Johnson & Johnson) vaccine).²⁹

Exploratory hypothesis H1c: A greater incidence of Veterans who complete seasonal flu vaccination.

Exploratory hypothesis H1d: Among those eligible for a COVID booster during the trial period, a greater incidence of Veterans completes at least one booster dose.

In addition, we will utilize the VA Corporate Data Warehouse (CDW) and other VA administrative data to assess other independent predictors of vaccine acceptance (e.g., sociodemographic, clinical, and health services utilization).

Specific Aim 2 During an 18-month period that overlaps the trial period, conduct surveys in a sociodemographically and clinically diverse purposive sample of Veterans (N=450) with primary care visits from VISN 16 and 21 Intervention and Usual Care sites who did (N=360) and did not (N=90) receive COVID-19 vaccination. The survey will examine predictors of COVID-19 vaccine acceptance and are organized according to the World Health Organization Behavioral and Social Drivers of Vaccination (BeSD) framework.³⁰ The survey includes questions from Centers for Disease Control and multiple VA surveys. In addition, in a smaller purposive subset of Veterans (N~90), we will conduct deeper-dive qualitative interviews to explore the following research questions:

- Did discussions with Veterans' HCPs influence their decisions to accept COVID-19 vaccination?
 - o If so, how important were these discussions compared to other factors?
 - o What was important about the HCP or these discussions regarding decision- making?
 - o How did this vary by Veteran subgroup?
 - Are Veterans more likely to report engaging in discussions about COVID- 19 vaccination at Intervention compared to Usual Care sites?
- Which factors (e.g., trust in VA HCPs, correct information about vaccines, prior experiences with VA healthcare, risk perception, perceived lack of time/access, and/ or discrimination) are most influential in Veterans' decision-making regarding COVID- 19 vaccination?
 - o How do these factors vary by Veteran subgroup: women, younger Veterans (< age 50), Black or African American, Hispanic/Latinx and Asian Pacific Islander Veterans, rural Veterans, and those with serious mental illness?
 - o Among Veteran subgroups, do these factors differ at VAI vs. Usual Care sites?

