Aim 1: This cluster RCT (with randomization at the site level) will be conducted at a maximum of 16 VAMCs or systems in VISNs 16 and 21: up to 8 VAMCs in each VISN that are willing and eligible to participate in the trial. (See Table 2 below for specific study site locations; see **Appendix Tables 1-3 for more detailed information about each study site**). VISNs 16 and 21 cover broad regions of the U.S. affording considerable geographic diversity. VISN 16 includes VAMCs and systems located in Arkansas, Louisiana, Mississippi, and Texas and VISN 21 covers Northern and Central California, Nevada, and Hawaii. This trial will include primary care clinics within each VAMC (i.e., Medical Practice, Geriatrics, Women's Clinic, Infectious Disease/HIV Clinic), as well as community-based outpatient clinics (CBOCs) and the patient-Aligned Care Team (PACT) staff within each CBOC and clinic. Aim 1 will focus on Veterans who have had a primary care visit within the past year at one of the primary care clinics or CBOCs affiliated with each of the participating VAMCs in VISNs 16 and 21. The primary aim of receiving any COVID-19 vaccination includes all veterans regardless of prior vaccination status while the secondary aim of primary vaccine series completion is restricted to veterans who remained unvaccinated at the start of the trial.

| Name | VISN | Station ID | Туре | Location | State |
|---|------|------------|------|---|-------|
| Alexandria VA Health Care System | 16 | 502 | VAMC | [name] | LA |
| Central Arkansas Veterans Healthcare System | | | | | |
| Eugene J. Towbin Healthcare Center | 16 | 598 | VAMC | [name] | AR |
| Central Arkansas Veterans Healthcare System John L. | | | | | |
| McClellan Memorial Veterans Hospital | 16 | 598 | VAMC | [name] | AR |
| G.V. (Sonny) Montgomery VA Medical Center | 16 | 586 | VAMC | [name] | MS |
| Gulf Coast Veterans Health Care System | 16 | 520 | VAMC | [name] | MS |
| Michael E. DeBakey VA Medical Center | 16 | 580 | VAMC | [name] | TX |
| Overton Brooks VA Medical Center & Shreveport | 16 | 667 | VAMC | [name] & | LA |
| | | | | [name] | |

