5.1.2 Secondary Outcome

The secondary outcome is completion of COVID-19 primary vaccination series by a previously unvaccinated Veteran with one or more primary care visit(s) at a participating VA facility within the past year.

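### The denominator correction for the secondary outcome is written in terms of series completion, but the outcome population is Veterans with no prior dose

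*SAP*

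**What the plan says.** Most of the text describes a population with no prior dose. SAP 5.1.2 defines the secondary outcome as "completion of COVID-19 primary vaccination series by a previously unvaccinated Veteran". Hypothesis H1b in Protocol 3.0 reads "A greater incidence of previously unvaccinated Veterans that completes COVID-19 primary vaccination", and Protocol 5.9 repeats that population. Protocol 5.2.b says the secondary aim is "restricted to veterans who remained unvaccinated at the start of the trial". Protocol 5.3 (Sample Determination for Aim 1) explains unvaccinated, in parentheses, as not having received at least one dose.

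The general description of the Bayesian model in SAP 9.1.4.2 follows the same idea. It corrects the "denominator at each facility due to misclassifying them as unvaccinated prior to study start".

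SAP 9.1.5.2 applies that model to the secondary outcome but changes the status. The uncertainty about eligibility becomes a matter of "knowing with 100% certainty that a Veteran did not complete the vaccine primary series prior to study start", and the quantity removed from the denominator is "the count of Veterans who were misclassified as having not completed the primary series at or before baseline". Protocol 5.9 carries the same sentences.

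The analysis set in SAP 9.1.5 is "Veterans reported to not have initiated or completed the COVID-19 primary series at randomization". The external-records analysis in SAP 9.1.5.1 uses Veterans "who were not reported to have completed or initiated the primary series at randomization".

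**The concern.** A Veteran who received one dose of a two-dose product outside VA before baseline, with no record in VA data, is labelled unvaccinated. By the outcome definition this Veteran does not belong in the denominator. The rule in SAP 9.1.5.2 removes hidden completers only, so the Veteran stays in.

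The purpose of this analysis is to show what the main secondary result would look like if baseline status were known. If it removes a different group from the one that the outcome definition excludes, it estimates completion in a different population, and a gap between the two results is harder to interpret.

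The choice of status also has to come before the prior. Under SAP 9.1.4.2 the misclassification rate follows a truncated Beta distribution whose lower bound comes from Medicare data and whose other features are set by the investigators. A rate of unrecorded doses and a rate of unrecorded completed series are different quantities, and the second cannot exceed the first.

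**Working it through.** The plan states no figure for the denominator correction, so there is nothing of its own to reproduce. The check is to compare the definitions and then illustrate the size.

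**Definitions.** Among Veterans labelled unvaccinated in VA data there are three true baseline states:

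| True state at baseline | Belongs under the no-dose definition (SAP 5.1.2) | Removed under SAP 9.1.5.2 |
|---|---|---|
| No dose | yes | no |
| Unrecorded partial series | no | no |
| Unrecorded completed series | no | yes |

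Only the middle row conflicts. It arises only for multi-dose products, because H1b counts one Janssen dose as a completed series.

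**Inputs.**
- *m*: share of labelled-unvaccinated Veterans who in truth had a prior dose. The documents do not give it; I assume 10%, 30% and 50%.
- *s*: share of those who were only part way through the series. The only figures in the documents that bear on it are in Protocol 2.0: 68% of the US population aged 12 and older with at least one dose and 58% fully vaccinated, August 2021. So *s* = (68 − 58)/68 = 10/68 = 14.7%. This is a general-population figure from before the 2022 site starts.

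**Formulas**, per Veteran labelled unvaccinated:
- Denominator under the no-dose definition: D = 1 − m.
- Denominator after removing completers only: D′ = 1 − m(1 − s).
- Wrongly left in: D′ − D = m·s.
- Excess: D′/D − 1.
- Relative shrinkage of a rate with the numerator fixed: 1 − D/D′.

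**Results with s = 14.7%, per 1,000:**

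| m | D | D′ | Left in | Excess | Shrinkage |
|---|---|---|---|---|---|
| 10% | 900 | 914.7 | 14.7 | 1.6% | 1.6% |
| 30% | 700 | 744.1 | 44.1 | 6.3% | 5.9% |
| 50% | 500 | 573.5 | 73.5 | 14.7% | 12.8% |

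With *s* varied from 5% to 25%, the extremes are:
- m = 10%, s = 5%: D′ = 905 against 900, an excess of 0.6% and shrinkage of 0.6%.
- m = 50%, s = 25%: D′ = 625 against 500, an excess of 25% and shrinkage of 20%.

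If *m* and *s* are equal in the two arms, the rate difference shrinks by the same factor as each rate. These are relative changes, not percentage points.

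**The alternative definition.** If eligibility means series not completed, the right denominator is 1 − m(1 − s). That is what SAP 9.1.5.2 produces, so the under-correction is zero.

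**The case against.** The best defence is that SAP 9.1.5.2 is loosely worded and does not set out a different estimator. It says that it reuses the model already described (citing a Section 9.1.4.3 that does not exist; the model is in 9.1.4.2), and that description concerns Veterans misclassified as unvaccinated. No rate is fixed, and SAP 9.1.4.2 promises results over a range of assumptions for the misclassification rates. A wide enough range might cover hidden partial series. All of this is fair, and it is why under-correction cannot be stated as fact. But varying a rate does not settle what the rate measures, and the rule specific to this outcome names completers only.

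A reader might infer two stronger points that the documents do not support.

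The first is that the main secondary analysis admits Veterans with one recorded dose, because the wording of SAP 9.1.5 and 9.1.5.1 can be parsed either way. The natural reading is that neither event had occurred; if one-dose Veterans were meant to be in, mentioning initiation would add nothing. The phrase deserves tightening but is not evidence of a different main population.

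The second is that one-dose Veterans complete more often, so that an imbalance between arms would shift the treatment difference by a predictable amount. The documents give neither completion rates by prior dose nor a one-dose share for the sites. That argument also concerns recorded one-dose Veterans. When the first dose is unrecorded, a later recorded dose may look like the first, and the completion may not be counted at all.

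**Conclusion.** The mismatch is real. The outcome definition, the protocol's population statements and the general model description all refer to unvaccinated Veterans, whereas SAP 9.1.5.2 and the matching text in Protocol 5.9 correct for series completion. Followed as written under the no-dose definition, the rule leaves Veterans with an unrecorded partial series in a denominator where they do not belong.

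Under-correction depends on two conditions: that the no-dose definition governs, and that the elicited rate counts completed series only. If both hold, the illustrative excess is 1.6% to 14.7%. That range rests on an assumed *m* of 10% to 50% and on a US share from August 2021. The shrinkage also requires an unchanged numerator and equal misclassification in the two arms. The true size cannot be found from the documents.

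The reach is narrow. The main secondary estimate does not use this correction. The primary outcome is also untouched, since its population includes all Veterans regardless of prior vaccination.

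**What to change.** In SAP 9.1.5.2 and the matching paragraph of Protocol 5.9, define the denominator reduction as the modelled number of Veterans with one or more unrecorded COVID-19 doses at baseline. Restate the eligibility uncertainty in the same terms, and elicit the prior, including its Medicare-based lower bound, for that status.

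In SAP 9.1.5 and 9.1.5.1, and in the same sentences of Protocol 5.9, reword the analysis set to Veterans who *had neither initiated nor completed* the primary series, meaning no recorded dose at baseline. Every section then uses the SAP 5.1.2 population. Correct the cross-reference to Section 9.1.4.3 in the same edit.

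The cost is a small wording change and one re-elicited prior. No new data or additional analysis is needed.
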